Indicate which of the following are employed as a part of screening or main study consent procedures

✓ Consent Form

Persons designated to discuss and document consent

Select the names of persons designated to obtain consent/assent

- [name]
- [name], MD
- [name]
- [name]
- [name], MD
- [name], MD
- [name], MD
- [name], MD
- [name]. MD
- [name]
- [name], MD

Type in the name(s) not found in the above list

Study Procedures

Describe the procedures required for this study

Potential subjects will undergo a screening visit which will include a demographics questionnaire, medical history, physical examination, psychiatric evaluation, laboratory testing, and electrocardiogram. The MINI International Neuropsychiatric Interview (MINI) will be conducted to determine current DSM-5 diagnoses. Eligible participants will be offered the opportunity to participate in the research treatment study, using the IRB-approved consent form obtained by the research psychiatrist.

This is an open-label pilot trial to evaluate the safety and tolerability of lofexidine in the management of opioid withdrawal symptoms while initiating outpatient treatment with naltrexone. The initiation procedure will be a flexible detoxification lasting 2 to 10 days concluding with the injection of XR-Naltrexone (Vivitrol). Lofexidine will be fixed-flexible dosing started on day 1 with maximum dose being three 0.18mg tablets taken orally 4 times daily at approximately 4-to 6-hour intervals. Lofexidine treatment will continue throughout the detoxification, up to 10 days, and will be discontinued with a gradual dose reduction over 2 to 4 days (Table 2). Precipitated withdrawal symptoms are treated with lofexidine, clonazepam, and other adjuvant medications as detailed below.

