The study will be entirely outpatient. Upon study entry, participants will begin clinic visits at the Substance Treatment and Research Service (STARS) clinic. After the detoxification period (2-10 days) where participants will attend the clinic daily, participants will then attend the clinic twice per week for the next 4 weeks and then once per week for the last 4 weeks. All participants will visit the clinic weekly to provide urine toxicology, report on adverse events, and complete additional assessments. All participants will also receive medical management, a medication adherence focused psychosocial intervention that facilitates compliance with study medication and other study procedures, and promotes abstinence from opioids and other substances.

Detoxification and Induction onto Injectable Naltrexone: The detoxification-naltrexone induction will be performed at the STARS outpatient research clinic, which is outfitted with a detoxification suite. After study consent and prior to initiating any study procedures, a urine will be collected and tested for pregnancy. A negative urine pregnancy is required at admission as detoxification and naltrexone treatment would not be recommended during pregnancy.

Participants come to the clinic daily for safety assessments, clinical monitoring, and management of withdrawal. Patients will be seen at the clinic preferably in the morning on Day 1 to initiate the lofexidine-naltrexone procedure. On Study Day 1, following the consent procedure, participants will start lofexidine and will be instructed to begin to abstain from opioids. Vital signs will be checked post 1 hour of initial lofexidine dose to see if there is an effect on blood pressure. Participants will continue to receive lofexidine 0.18mg #3 QID (approximately 9am, 1pm, 5pm, 10pm). Administration of lofexidine is withheld in case of dizziness or lightheadedness complaints, low blood pressure (SBP < 90 or DBP < 60), or orthostatic blood pressure changes (from lying down to standing up drop of SBP \geq 20 mmHg, DBP \geq 10 mmHg). If there are

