Naloxone challenge and Vivitrol injection: The purpose of the naloxone challenge is to determine if the participant is likely to tolerate a Vivitrol injection. The timing of naloxone challenge is based on a number of clinical factors including time since the last opioid use, pattern of recent opioid use, severity of tolerance and withdrawal symptoms, and response to ancillary medications used for the treatment of withdrawal. We will make the decision to administer naloxone on the COWS score, as well as the other factors noted above. The COWS score may be suppressed by other medications, and could also be suppressed by use of opioids. Therefore a global assessment of the participant's progress through the induction period will be taken into account when deciding to administer naloxone, using the COWS as the final indicator of readiness. **If a participant reports continued use of opioids, then naloxone challenge will not be administered because it would be very likely to precipitate withdrawal. However, if the urine test for opioids is positive, but the patient reports not having used any opioids in the recent days, then clinical judgment will be exercised as to whether to administer the naloxone challenge. This judgment would balance the risk of a brief episode of withdrawal precipitated by naloxone, against the potential benefit that the patient passes the naloxone challenge (no exacerbation of withdrawal symptoms) can receive injection naltrexone.**

Once a participant has a COWS < 6, they qualify for a naloxone challenge. Discussion of the naloxone challenge risks/benefits will be discussed with study staff and the naloxone consent form will be signed prior to the challenge. The challenge will be conducted over a 60 minute time frame. Individuals will be asked the last opioid use, route, and amount. A naloxone dose of 0.8mg will be given as an injection in the participants upper arm muscle. Participants will then be monitored for withdrawal and changes in vital signs for the next 60 minutes using the standard COWS (5 minutes, 20 minutes, and 60 minutes after naloxone dose). Once the participant completes the naloxone challenge and has no increase in COWS withdrawal score ≥ 10 they may receive XR-naltrexone injection (Vivitrol 380mg) on Day 2-10. Following the naltrexone injection, the patient will be required to remain at the clinic for at least 1 hour prior to discharge, to monitor for any increased withdrawal symptoms or side effects.

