This outpatient detoxification/naltrexone induction medication protocol is outlined in Table 2, below. Evaluation of withdrawal severity (COWS) and vital signs, will be obtained at least twice per day (at the beginning and end of their study visit). Additional COWS can be administered as per clinical judgment of the study physician and nurse practitioner.

For female participants, a urine pregnancy test will be obtained on the day of each vivitrol administration. If at any time during the study a female participant has a positive urine pregnancy test, this will be reported to the IRB and the study sponsor, US WorldMeds and the participant will be discontinued from the study. We will follow our study discontinuation procedure as outlined below to transition these individuals to a treatment program in the community.

Outpatient Treatment Post-Detoxification

Study Visits

Participants will have two weekly clinic visits during the first month of treatment and one weekly visit during the second month. At each visit the patient meets with the research assistant to complete research ratings, including self-report of withdrawal, mood, and drug use. The patient provides a urine sample under observation by a staff member at each visit. The sample is tested immediately for opioids. Vital signs are also taken. Once a week participant will meet with a study psychiatrist for safety and tolerability evaluation, along with medical management therapy.

Participants may come to the clinic to be seen as frequently as needed. In particular, any participant who is experiencing protracted opioid withdrawal will be offered clinical contact on a frequent, even daily, basis. For clinical matters arising in the evenings or on weekends, participants will have access to the 24-hour emergency telephone service, staffed by physicians familiar with this protocol who can address patients' concerns.

Outpatient medications

On the day after the XR-naltrexone injection participants will receive tapering doses of lofexidine for 2-4 days. During the subsequent 8-week course of outpatient treatment, patients receive additional injection of Vivitrol 380 mg, at week 4.

Medication Management

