Baseline demographics and non-efficacy outcomes, including retention, frequency of adverse events, and receipt of the first injection of naltrexone-xr will be tabulated and summarized for this open-label treatment group using means, standard deviations and percentages where appropriate. Opioid use (Timeline Follow-Back), craving for opioids (VAS scale), urine toxicology, and depression scores (HAMD) during detoxification and post detoxification will also be analyzed using similar models as in the primary hypothesis. PROC GLIMMIX in SAS® 9.4 will be used to conduct all analyses. All statistical tests will be two-sided with a level of significance of 5%.

Hypotheses testing:

Primary Hypothesis: Lofexidine will be associated with reduced symptoms of opioid withdrawal during the 2-10 days induction phase as compared to baseline (day 1).

To analyze the primary hypothesis, withdrawal severity (COWS) during the 2-10 days induction phase will be summarized using descriptive summaries and analyzed using longitudinal generalized linear mixed effects models with a main effect of time, adjusted by the baseline (day 1) withdrawal score. Based on the distribution of the outcome corresponding link function will be used (eg. log for skewed data etc). A random intercept will be used to account for the between subject variances and an autoregressive (AR1) covariance structure to account for the correlation of the repeated observations within subjects over time.

Secondary Hypotheses: Lofexidine used to manage opioid withdrawal symptoms will result in successful initiation of outpatient naltrexone-XR treatment by the completion of the induction phase and patients receiving first naltrexone-xr injection.

To analyze the secondary hypothesis, the proportion of subjects who complete the induction phase and receive the first naltrexone-xr injection will be calculated. A one-sample proportion test will be used to compare whether the sample proportion is significantly different from benchmark proportions of successful induction to naltrexone-xr. Additionally, 95% confidence interval will be computed to estimate the expected range of population proportion of successful induction.

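### The primary hypothesis is a comparison with Day 1, but the planned test is a time effect adjusted for Day 1, and no Day 1 contrast is specified

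*Combined protocol and SAP*

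**What the plan says.** The *Overview of Data Analytic Plan* (Hypotheses testing) gives the primary hypothesis as: "Lofexidine will be associated with reduced symptoms of opioid withdrawal during the 2-10 days induction phase as compared to baseline (day 1". The analysis is a descriptive summary plus COWS "analyzed using longitudinal generalized linear mixed effects models with a main effect of time, adjusted by the baseline (day 1) withdrawal score", with a random intercept and AR(1) errors. Tests are two-sided at 5%. The link is to be chosen from the outcome's distribution.

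The plan does not say whether time is linear or categorical, whether Day 1 is an outcome record, or which estimate from the model answers the hypothesis. No other section supplies a Day 1 contrast.

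The phase itself can be read in two ways. *Study Procedures* describes "a flexible detoxification lasting 2 to 10 days", which is a duration. The subsection on the naloxone challenge says of participants who pass that "they may receive XR-naltrexone injection (Vivitrol 380mg) on Day 2-10", which is a range of day numbers.

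**The concern.** The hypothesis concerns the level of COWS after Day 1 relative to Day 1. A main effect of time answers a different question, and which one depends on the reading.

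- **Reading 1: outcomes are the days after Day 1, and Day 1 is only a covariate.** The time effect compares the later days with each other. It can miss a reduction that is complete by Day 2. It can also be significantly downward after an early rise, although mean COWS was never below Day 1.
- **Reading 2: Day 1 is also an outcome.** Day 1 is then both response and covariate. The time effect is either a linear trend or an omnibus test that a rise above Day 1 can also trigger.

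An early rise is possible here because on Day 1 "participants will start lofexidine and will be instructed to begin to abstain from opioids". Withdrawal can therefore build after the baseline score.

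If the time effect is reported as the primary result, a real early reduction could be called non-significant, or a fall from an early peak could be called a benefit.

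**Working it through.** **Inputs.** The documents give no SD, COWS profile, effect size or power calculation, so there is no stated figure to reproduce. The sample sizes are 10 completers and 20 enrolled (*Description of Subject Population*). All COWS values, SDs and correlations below are assumptions.

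**Step 1: algebra under Reading 1.** For days t after Day 1,

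g(E[COWS_it]) = α + β·COWS_i1 + τ_t + b_i.

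Replace COWS_i1 by COWS_i1 + c. The same fit is obtained with α replaced by α − βc. Every τ_t, its standard error and its p-value are unchanged. This holds for any link if the Day 1 score enters untransformed. The quantity in the hypothesis, δ = mean(later days) − Day 1, moves by −c.

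One simulated trial with n = 20 shows this:

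| Shift in all Day 1 scores | Time p, day as category | Time p, linear | Day 1 contrast |
|---|---|---|---|
| −6 | 0.62 | 0.46 | +5.7 (p<0.001) |
| 0 | 0.62 | 0.46 | −0.3 (p=0.61) |
| +6 | 0.62 | 0.46 | −6.3 (p<0.001) |

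**Step 2: complete data.** There were 4000 runs per cell, with between-subject SD 3, within-subject SD 3 and AR(1) ρ = 0.5. Tests were t-tests on per-participant slopes over Days 2–10 and on per-participant mean(Days 2–10) − Day 1. Percentages are for n = 10 / n = 20.

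| Assumed means | True slope per day | True contrast | Slope significant | Contrast significant |
|---|---|---|---|---|
| 12, then 8 throughout | 0 | 8 − 12 = −4 | 4.8 / 5.2% | 94.4 / 100%, lower |
| 8, then 14 falling to 8 | (8 − 14)/8 = −0.75 | 11 − 8 = +3 | 98.6 / 100%, falling | 77.2 / 98.6%, higher; 0% lower |
| 12, then 11.5 falling to 6 | (6 − 11.5)/8 = −0.69 | 8.75 − 12 = −3.25 | 96.1 / 100%, falling | 84.3 / 99.6%, lower |
| Flat | 0 | 0 | 5.4 / 4.8% | 5.1 / 4.7% |

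Rows 2 and 3 have nearly the same slope but contrasts of opposite sign.

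**Step 3: planned covariance structure with early exit.** There were 1000 trials per cell, with random intercept and AR(1) fitted by REML and COWS in whole numbers floored at zero. Exit followed the first post-Day-1 COWS below 6. This simplifies the protocol's rule: "Once a participant has a COWS < 6, they qualify for a naloxone challenge". Ranges cover four sets of between SD / within SD / ρ: 3/3/0.5, 2/4/0.3, 4/2/0.7 and 4/4/0.5. Time tests used containment degrees of freedom. The contrast used n − 1 and the day categories set out in the fix. Cells show n = 10; n = 20.

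| Profile | Reading 1, category | Reading 1, slope falling | Day 1 contrast |
|---|---|---|---|
| (a) 12, then 7 | 8–15%; 8–11% | – | 84–100%; 98–100% |
| (b) 7, 14 on Day 3, 7 on Day 10 | – | 48–89%; 65–100% | reduction 0%; 0% |
| (c) steady 12 to 5 | 43–99%; 75–100% | 77–100%; 96–100% | 37–95%; 69–100% |
| Flat, mean 9 | 7–9%; 5–9% | – | 2.5–5%; 4–5% |

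**Step 4: Reading 2, Day 1 covariate kept.** The category test was significant in 69–100% and 96–100% for (a), but also in 87–100% and about 100% for the rise in (b). Linear time was significantly downward in 52–82% and 67–98.5% for (a), and in 0–3% for (b).

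**Step 5: is the contrast estimable?** In (a), nobody remained on Day 10 in 0.2–27% of trials (n = 10) and 0–9% (n = 20), so a contrast weighting every day equally can fail. With pooled late days and a merge rule it was estimable in every trial. The merge was needed in 4–46% and 0–6% of trials. Adding 7% random daily dropout (600 trials per cell) left it always estimable, with flat-COWS rejection of 4–5% and 4–6%.

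**The case against.** The strongest reply is that this is an overview that names a model and a factor and does not say that only the overall time p-value will be reported. If Day 1 is an outcome and day is categorical, a Day 1 contrast can be computed from the same fit. There is some support for that reading: *Compensation and/or Reimbursement* allows up to $200 for detoxification at $20 a visit, and 200/20 = 10 visits, which fits Day 1 lying inside the phase. Under Reading 2 an early drop is usually detected. The percentages rest on assumed values, the exit rule is simplified, and the time tests and the contrast used different degrees of freedom. A two-sided contrast would also be significant for a rise. The planned slope is more sensitive in a steady decline. Finally, the only stated Aim is safety and tolerability.

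Much of this stands. The percentages are illustrations, the slope does better in profile (c), and the consequence is limited. Three parts do not answer the point. Ten paid visits do not settle the reading, because Day 1 can lie inside the phase and still enter only as a covariate. A contrast that could be derived is not one that has been specified: each day, the last day or an average are all possible, and choosing after seeing the data undermines a 5% test. A significant contrast carries a sign, whereas the omnibus test does not. The descriptive summaries may show the pattern but do not test it.

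**Conclusion.** The concern holds. As written, the test named for the primary hypothesis does not test it. Under Reading 1 the time effect carries no information on whether COWS is above or below Day 1. That result is algebraic and needs only that Day 1 enters untransformed. Under Reading 2 it is a trend or a directionless test, with Day 1 on both sides of the model.

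The size of the error depends on the COWS profile, which the documents do not give. Under the assumed values it ranges from almost complete loss of sensitivity (profile a) to a misleading downward finding in most trials (profile b). In a steady decline there is no loss.

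This should be fixed before analysis. It is not critical: the trial is a small uncontrolled pilot and no go/no-go decision is tied to this p-value.

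**What to change.** Replace the primary-analysis sentence with wording such as:

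> COWS is the repeated outcome and the pre-dose Day 1 score is its first value; Day 1 is not a covariate. Day is a category: 1, 2, 3, 4, 5 and 6–10 pooled. If fewer than 3 participants contribute to the last category, it is merged with the one before, repeated as needed. The model keeps the random intercept and AR(1). The primary test is one contrast, the equally weighted mean of the post-Day-1 categories minus Day 1, two-sided at 5%, reported with its sign, 95% CI and small-sample degrees of freedom (n − 1 or Kenward-Roger). A reduction is claimed only if the estimate is below zero.

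The cut points, minimum number and weights are an example; the team should fix its own before analysis. Weighting the late pool by its number of days trades sensitivity: at n = 10 it gave 73–100% in (a), 55–98% in (c) and 3–6% when flat. Modelling change from Day 1 with a centred Day 1 score, and testing the adjusted mean change against zero, would also serve if the averaging over days is named.

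In addition:

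- Use the likelihood-based model rather than a raw mean change, because exit depends on COWS, and show the number still in induction each day.
- With a log link, report a ratio of means.
- State which daily COWS reading is used, unless the study assessments table already does. COWS is taken at least twice a day and lofexidine starts on Day 1.
- The SAP applies similar models to opioid use, craving, urine toxicology and HAM-D. Carry the contrast over only where a Day 1 comparison is intended.

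The cost is SAP wording and some sensitivity in a steady decline. Data and software are unchanged.
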